10.3 Electronic Patient Reported Outcomes (ePRO)

Patient reported data must be completed for each subject screened/enrolled in this study. Some of these data are being collected with an Electronic Patient Reported Outcome (ePRO) system called Trialmax, provided by the technology vendor CRF Health of Plymouth Meeting, PA, USA. The ePRO system is in compliance with Title 21 CFR Part 11. The documentation related to the system validation of the ePRO system is available through the vendor, CRF Health, while the user acceptance testing of the study-specific PRO design will be conducted and maintained at AbbVie.

The subject will be entering the data on an electronic device; these data will be uploaded to a server. The data on the server will be considered source and maintained and managed by CRF Health.

Internet access to the ePRO data will be provided by CRF Health for the duration of the trial. This access will be available for the duration of the trial to the site investigator, as well as delegated personnel. Such access will be removed from investigator sites following the receipt of the study archive. Data from the ePRO system will be archived on appropriate data media (CD-ROM, etc.) and provided to the investigator at that time as a durable record of the site's ePRO data. It will be possible for the investigator to make paper print-outs from that media.

The ePRO data (IBDQ, SF-36, PGIC, PGIS, FACIT-F, WPAI, EQ-5D-5L, UC-SQ [UC-SQ only in select sites during Substudy 1]) will be collected electronically via an onsite device at visits specified in [Appendix C](#) and [Appendix E](#). Stool information, abdominal pain, bowel urgency, use of anti-diarrheals and endoscopy prep will be collected electronically via a handheld device provided to the subject. The electronic device will be programmed to allow data entry once per day. All data entered on the device will be immediately stored to the device itself and manually/automatically uploaded to a central server administrated by CRF Health. The investigator and delegated staff, will be able to access all uploaded patient entered data via a password protected website, up until the generation, receipt and confirmation of the study archive.

COVID-19 Pandemic-Related Acceptable Protocol Modifications

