Appendix H. Mayo Scoring System for Assessment of Ulcerative Colitis Activity

The Mayo Scores range from 0 to 12, with higher scores indicating more severe disease. It consists of 4 subscores. Each sub-score ranges from 0 to 3. The 4 components of the Mayo Score are:

Stool Frequency: 0 = Normal number of stools for this subject 1 = 1 – 2 stools more than normal 2 = 3 – 4 stools more than normal 3 = 5 or more stools more than normal

Rectal Bleeding: 0 = No blood seen 1 = Streaks of blood with stool less than half the time 2 = Obvious blood with stool most of the time 3 = Blood alone passed

Findings on Endoscopy: 0 = Normal or inactive disease 1 = Mild disease (erythema, decreased vascular pattern) 2 = Moderate disease (marked erythema, lack of vascular pattern, any friability, erosions) 3 = Severe disease (spontaneous bleeding, ulceration)

Physician's Global Assessment: 0 = Normal 1 = Mild disease 2 = Moderate disease 3 = Severe disease

Note: In Study M14 -234 Substudy 2 and Substudy 3, evidence of friability during endoscopy in subjects with otherwise "mild" endoscopic activity will confer an endoscopic subscore of 2.

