4.5 Derived, Defined and Transformed Variables

The following defined variables will be used:

- Full Mayo Score
 - Full Mayo Score is defined as the composite score of UC disease activity based on the subscores of stool frequency (0 – 3), rectal bleeding (0 – 3), physician's global assessment (0 – 3) and endoscopy (0 – 3). This score ranges from 0 – 12 points with higher scores representing more severe disease (also see Section 6.0 for the rules for calculation of rectal bleeding and stool frequency subscores). A description of the Mayo Scoring System can be found in Appendix H of the protocol.
 - Clinical Response per Full Mayo Score is defined as a decrease in Full Mayo Score of ≥ 3 points and $\geq 30\%$ from Baseline, PLUS a decrease in the rectal bleeding subscore [RBS] ≥ 1 or an absolute RBS of 0 or 1.

- Clinical Remission per Full Mayo Score is defined as Full Mayo Score ≤ 2 with no subscore > 1 .
- Partial Mayo Score
 - Partial Mayo Score is defined as the composite score of UC disease activity based on the subscores of stool frequency, rectal bleeding, and physician's global assessment and DOES NOT include the endoscopy subscore. This score ranges from 0 – 9 points (also see Section 6.0 for the rules for calculation of rectal bleeding and stool frequency subscores).
 - Response per Partial Mayo Score is defined as a decrease in Partial Mayo Score ≥ 2 points and $\geq 30\%$ from Baseline, PLUS a decrease in RBS ≥ 1 or an absolute RBS of 0 or 1.
 - Remission per Partial Mayo Score is defined as Partial Mayo Score ≤ 2 , with no subscore > 1 .
- Adapted Mayo Score
 - Adapted Mayo Score is defined as Full Mayo Score minus the Physician's Global Assessment (PGA) subscore. This score ranges from 0 – 9 points.
 - Remission per Adapted Mayo Score is defined as an Adapted Mayo Score ≤ 2 , with stool frequency subscore ≤ 1 , RBS of 0, and endoscopic subscore ≤ 1 .
 - Response per Adapted Mayo Score is defined as a decrease in the Adapted Mayo Score ≥ 2 points and $\geq 30\%$ from baseline, PLUS a decrease in RBS ≥ 1 or an absolute RBS ≤ 1 .
- Endoscopic Remission: Endoscopic subscore of 0
- Endoscopic Improvement: endoscopy subscore of 0 or 1

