The diary entries on the days the subjects take endoscopy preparation medications, the day of endoscopy procedure, and 2 days after endoscopy procedure will be excluded. If a subject takes an antidiarrheal on a day, the stool frequency subscore is considered as 3 for that day. For the calculation of the stool frequency subscore and the rectal bleeding subscore at each visit, the most recent consecutive 3-day period prior to the study visit will be used.

If diary entries from the 3 consecutive days prior to the visit are not available, the average of the entries from the most recent 3 non-consecutive days will be utilized. If less than 3 days of diary data are available, stool frequency and rectal bleeding subscores will be considered missing.

Rounding to one decimal place will be applied to the calculation above for the subscores, Adapted Mayo Score, Partial Mayo Score and Full Mayo Score.

The last day of the days used for stool frequency and rectal bleeding subscore calculation will be used to decide the actual visits that should be assigned to the Mayo Score and Partial Mayo Score data.

Definition of Prior Medications

Prior medications include all medications with an end date before the first study drug dose date, and the medications with start date prior to the first dose date but end date missing.

Definition of Medication Use at Baseline

Medications are considered to be used at Baseline if the medication start date is on or before the first study drug dose date and the medication end date is on or after the

first dose date. All medications with a start date after the first dose date or an end date before the first dose date are excluded.

Definition of Concomitant Medications

Concomitant medications include medications with a start date prior to the Baseline date which are continuing after Baseline and all medications with a start date between the Baseline date and last study drug administration + 1 day. All medications with an end date prior to the first dose date are excluded.

If the start date is completely missing for a medication and if the stop date is before the baseline date, it is considered previous medication and not further evaluated. In addition to start date being completely missing, if the stop date is also completely missing or the stop date is on or after the baseline date, it will also be considered as a concomitant medication.

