10.2 Primary Efficacy Analyses

This section provides the details of the primary efficacy analysis for Substudy 1.

Primary Efficacy Endpoint:

Proportion of subjects who achieve clinical remission per Adapted Mayo score (defined as stool frequency subscore (SFS) ≤ 1 , rectal bleeding subscore (RBS) of 0, and endoscopic subscore ≤ 1) at Week 8.

Analysis Data Set for the Primary Efficacy Analysis:

The primary efficacy analysis will use the ITT1A analysis data set.

Imputation Method Used for the Primary Efficacy Analysis:

The primary efficacy analysis will use the NRI method to impute the missing values at Week 8 for Substudy 1.

Statistical Method of the Primary Efficacy Analysis:

The comparisons between an ABT-494 treatment group and placebo on the primary efficacy endpoint will be performed using MCP-Mod approach in the ITT1A analysis set.

The dose-response relationships among the four ABT-494 treatment groups and placebo group will be characterized for the primary endpoint at Week 8 using MCPMod approach. The following models will be considered: log-linear, E_{\max} , exponential, logistic and $\text{sig}E_{\max}$, Quadratic. The MCPMod approach for trial analysis stage consists of two main steps: MCP and Mod step. The MCP step focuses on establishing evidence for a drug effect across the doses, i.e., detecting a statistically significant dose response signal for the clinical endpoint and patient population investigated in the study. This step will typically be performed using an efficient test for trend, adjusting for the fact that multiple candidate dose response models are being considered. If a statistically significant dose response signal has been established at significance level of 0.05 using two-sided test, one proceeds with determining a reference set of significant dose response models by discarding the non-significant models from the initial candidate set.

The response function will be the log odds (logit) of the proportion of subjects with endoscopic/clinical remission. The fitted curve will be shown graphically with confidence intervals for each dose. Estimates of the treatment differences in the response function and associated 95% confidences for each active dose against placebo will be calculated from the model. These results will be back-transformed to give point estimates of the difference in proportions and associated 95% confidence intervals.

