The pairwise comparisons for the difference in proportions of subjects between the treatment groups and placebo group will be performed using the Cochran-Mantel-Haenszel (CMH) test and will be stratified by previous biologic use, baseline corticosteroid use and baseline Adapted Mayo score (≤ 7 and > 7). Additionally, the CMH-based 95% confidence interval for the difference in proportions will be provided.

Sensitivity Analyses for the Primary Efficacy Endpoint:

- Hybrid multiple imputation method, as described in Section 6.0, will be to impute missing data.
- The last observation carried forward (LOCF) method will be used to impute missing data.
- Analysis of the primary endpoint will be conducted excluding the ITT1A subjects who did not meet inclusion/exclusion criteria.

As a sensitivity analysis, the clinical remission endpoint will also be summarized using the worst rectal bleeding subscore instead of the average rectal bleeding subscore. For this analysis, the rectal bleeding subscore will be calculated as the worst score during the most recent consecutive 3-day period prior to the study visit. If diary entries from the 3 consecutive days prior to the visit are not available, the worst value of the entries from the most recent 3 non-consecutive days will be utilized. If less than 3 days of diary data are available, rectal bleeding subscore will be considered missing.

In addition, an exploratory analysis of clinical remission at Week 8 will be conducted using the definition of stool frequency subscore (SFS) ≤ 1 , rectal bleeding subscore (RBS) of 0, and endoscopic subscore of 0.

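### Substudy 1's worst-rectal-bleeding sensitivity analysis is identical by construction to the primary remission analysis, so its agreement is not evidence of robustness to diary averaging

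*SAP*

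**What the plan says.** The primary endpoint in Section 10.2 of the Substudy 1 SAP is remission at Week 8, defined as SFS of at most 1, "rectal bleeding subscore (RBS) of 0" and an endoscopic subscore of at most 1. Section 4.5 adds a condition on the total Adapted Mayo score (at most 2).

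Section 6.0 gives the scoring rules for both diary items. For each visit, "the most recent consecutive 3-day period prior to the study visit will be used". If those days are not available, the three most recent non-consecutive days are averaged. With fewer than three days the subscore is missing. "Rounding to one decimal place will be applied to the calculation above for the subscores". Diary days used for endoscopy preparation, the endoscopy day and the two days after it are excluded. A day with antidiarrheal use is scored 3 for stool frequency.

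Under its sensitivity analyses, Section 10.2 says that "the clinical remission endpoint will also be summarized using the worst rectal bleeding subscore instead of the average rectal bleeding subscore". It then repeats the three-day window, the non-consecutive fallback and the rule for fewer than three days, with worst in place of average. It does not repeat the endoscopy-related exclusions.

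**The concern.** A sensitivity analysis is useful only if it could give a different answer from the primary analysis. This one changes how three RBS values are summarised, but the remission rule then asks only whether the summary is 0. At that cut-off the average and the maximum of non-negative scores carry the same information.

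If the analysis is run as planned, it will reproduce the primary remission counts in every arm. A report listing it among the sensitivity analyses could lead a reader to conclude that remission had been shown not to depend on averaging the diary. That dependence would not have been tested. It sits in SFS, where the cut-off is above 0 and one high day can be offset by two low ones.

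**Working it through.** **Inputs**

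- Daily item scale: Protocol Appendix H lists categories 0, 1, 2 and 3 and says "Each sub-score ranges from 0 to 3".
- Entries per day: Protocol Section 10.3 says "The electronic device will be programmed to allow data entry once per day", so each scoring day gives one whole number.
- RBS cut-off: exactly 0 (Substudy 1 SAP 10.2).
- SFS cut-off: three-day average of at most 1 (10.2 with 6.0).
- Rounding: one decimal place (6.0).
- Window, fallback and missing-data rule: the same in 6.0 and in the worst-RBS text of 10.2.

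**Step 1. RBS: average against worst.** Let the three daily scores be a, b and c, each at least 0.

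- (a + b + c)/3 = 0 holds if and only if a = b = c = 0, which holds if and only if max(a, b, c) = 0.
- Rounding does not break this. The smallest non-zero sum is 1, and 1/3 rounds to 0.3, not 0.
- Of all 4 × 4 × 4 = 64 three-day patterns, the two rules classify 0 differently, with or without rounding.

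**Step 2. The full remission rule.** Combining 64 RBS patterns, 64 SFS patterns and 4 endoscopic subscores gives 64 × 64 × 4 = 16,384 combinations. The total-score condition of Section 4.5 adds nothing: once SFS is at most 1, RBS is 0 and endoscopy is at most 1, the total is at most 1 + 0 + 1 = 2. The number classified differently by average RBS and worst RBS is 0.

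**Step 3. Missing data.** Both versions set RBS to missing under the same condition, so non-responder imputation (NRI) applies to the same subjects. Rates, differences and intervals are unchanged.

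**Step 4. SFS, where averaging can matter.** An average of at most 1 means a three-day sum of at most 3.

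| Sum | Patterns |
|---|---|
| 0 | 1 |
| 1 | 3 |
| 2 | 6 |
| 3 | 10 |
| Total | 20 |

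Patterns with every day at 0 or 1 number 2 × 2 × 2 = 8. The other 20 − 8 = 12 contain a day scored 2 or 3: three orderings of (0, 0, 2), six of (0, 1, 2) and three of (0, 0, 3). For example, 0, 0, 3 averages 1.0 and passes, including when the 3 comes from the antidiarrheal rule.

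Under the full rule, remission is met by 1 RBS pattern × 20 SFS patterns × 2 endoscopic subscores = 40 combinations. A worst-day SFS rule would reclassify 12 × 2 = 24 of them. These are counts of possible patterns, not proportions of subjects.

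**Step 5. Other planned analyses.**

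- The exploratory remission definition in 10.2 tightens endoscopy to 0 and keeps average SFS at most 1.
- The all-zero endpoint in 10.3 requires SFS, RBS and endoscopy all to be 0. Set against the exploratory definition, it differs only in the SFS cut. It excludes every subject with any SFS day above 0, so it gives a strict bound among subjects with an endoscopic subscore of 0. It moves the threshold and does not test averaging at the threshold of 1.

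**The case against.** The best reply is that little depends on this. It is one supplementary summary in a Phase 2b substudy. It feeds no dose-response model and no multiplicity step, and other sensitivity analyses remain: hybrid multiple imputation, last observation carried forward, and exclusion of subjects who did not meet entry criteria. Substudy 1 is closed and the induction dose has been chosen. All of this stands, and it sets the severity.

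It can also be said that the three-day average is the protocol's own definition of the score, so requiring every day to be at most 1 creates a stricter endpoint. That stands too. Averaging SFS is not an error, and a worst-day version belongs beside the primary analysis as a supplement.

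A third reply is that the identity rests on an assumption, because Section 10.2 does not restate the endoscopy-related day exclusions of 6.0. This is correct. If those exclusions were dropped, results could differ, but because different days were scored and not because worst replaced average.

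Three stronger readings are tempting, and the documents do not support them.

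- A reader might infer that SFS averaging goes wholly unexamined. The comparison of the all-zero endpoint with the exploratory definition gives a bound, so that goes too far.
- A reader might infer that a large share of remitters had a bad stool-frequency day. The documents contain no daily diary distribution, and any percentage follows from what is assumed. With four assumed daily distributions having 10% to 30% of days at 2 or more, the share of subjects passing the SFS rule who have such a day is about 21% to 41% if days are independent. It falls to about 9% to 18% if each day repeats the previous score with probability 0.5, and to about 5% to 10% if that probability is 0.7. These shares also condition on passing SFS alone, not on remission. None is an estimate for this trial.
- A reader might infer that the primary remission rates are biased. They follow the prespecified definition, and nothing here changes them.

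**Conclusion.** The worst-RBS analysis cannot disagree with the primary remission analysis, so it does not do what the SAP's label says. The conclusion rests on whole-number daily scores from 0 to 3, an RBS cut-off of exactly 0, and the same eligible diary days in both versions. The first two are stated in the documents; the third is their natural reading.

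Agreement between the two analyses should not be reported as robustness to diary averaging. The only route by which averaging can change remission status is SFS, and how many subjects that concerns cannot be determined from the documents. The consequence is one uninformative Phase 2b summary, which makes this a low-severity correction.

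**What to change.** In Section 10.2 of the Substudy 1 SAP, remove the worst-RBS analysis, or keep it with a statement that it is identical to the primary analysis by construction. In its place, plan a labelled supplementary summary of remission with SFS at most 1 on the worst of the same three scoring days, RBS of 0 and endoscopic subscore at most 1, using NRI. State that the day exclusions, fallback and missing-data rule of Section 6.0 apply. Leave the primary definition as it is. If the SAP can no longer be amended, label the summary as post hoc in the report and do not cite the worst-RBS result as support.

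The cost is a short text change and one re-derivation from diary data already collected. The supplementary remission rates may be lower than the primary rates and cannot be higher, because a worst day of at most 1 implies an average of at most 1.

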10.3 Secondary Efficacy Analyses

For the analysis purpose, the secondary efficacy endpoints are divided into two groups: (1) ranked secondary endpoints and (2) additional, non-ranked endpoints. The second group includes all other additional secondary variables. All analyses of secondary endpoints will be performed using the ITT1A analysis set of Substudy 1.

Ranked secondary efficacy variables (ranked hierarchically in decreasing order) for Substudy 1 are:

1. Proportion of subjects with endoscopic improvement (defined as an endoscopic subscore ≤ 1) at Week 8
2. Proportion of subjects achieving clinical remission per Full Mayo score (defined as a Full Mayo score ≤ 2 with no subscore > 1) at Week 8
3. Proportion of subjects achieving clinical response per Adapted Mayo score (defined as decrease from baseline in the Adapted Mayo score ≥ 2 points and $\geq 30\%$ from baseline, PLUS a decrease in rectal bleeding subscore (RBS) ≥ 1 or an absolute RBS ≤ 1) at Week 8
4. Proportion of subjects achieving clinical response per Partial Mayo score (using the Mayo Scoring System for Assessment of Ulcerative Colitis Activity, excluding endoscopic subscore; clinical response defined as decrease from baseline in the Partial Mayo score ≥ 2 points and $\geq 30\%$ from baseline, PLUS a decrease in rectal bleeding subscore (RBS) ≥ 1 or an absolute RBS ≤ 1) at Week 2
5. Change in Full Mayo score from Baseline to Week 8
6. Proportion of subjects with endoscopic remission (defined as an endoscopic subscore of 0) at Week 8
7. Proportion of subjects who achieved histologic improvement (defined as decrease from baseline in Geboes score) at Week 8

The additional, non-ranked endpoints include:

- Proportion of subjects who achieve clinical remission per Adapted Mayo score over time.
- Proportion of subjects achieving clinical remission per Partial Mayo score over time.

- Proportion of subjects achieving clinical remission defined as stool frequency subscore ≤ 1 , rectal bleeding subscore of 0, and endoscopic subscore ≤ 1 with absence of friability over time.
- Proportion of subjects achieving clinical remission defined as stool frequency subscore of 0, rectal bleeding subscore of 0, and endoscopic subscore of 0 over time.
- Proportion of subjects achieving clinical response per Partial Mayo score over time.
- Proportion of subjects with stool frequency subscore ≤ 1 over time.
- Proportion of subjects with rectal bleeding subscore of 0 over time.
- Proportion of subjects with fecal calprotectin below 150 mg/kg over time.
- Proportion of subjects with IBDQ response (increase of IBDQ ≥ 16 from Baseline) over time.
- Change from Baseline in hs-CRP over time.
- Change from Baseline in fecal calprotectin over time
- Change from Baseline in Adapted Mayo score, Full Mayo score, Partial Mayo score and Mayo subscores over time.
- Change from Baseline in UCEIS score over time.
- Proportion of subjects with histologic remission (defined as Geboes score < 2) at Weeks 8 and 44.
- Change from Baseline in histologic score over time.
- Change from Baseline in laboratory and nutritional parameters (e.g., hemoglobin, hematocrit, albumin, total protein concentration, and weight).
- Change from Baseline in subject-reported stool frequency (absolute values).
- Change from Baseline in IBDQ score over time.
- Change from Baseline in EQ-5D-5L score over time.
- Change from Baseline in WPAI scores over time.
- Change from Baseline in SF-36 PCS, MCS components and domain scores over time.
- Change in PGIC score over time.

- Change from Baseline in FACIT-F score over time.
- Change from Baseline in UC-SQ score over time
- Health care resource utilization (UC-related hospitalizations and surgeries) during the study.

For categorical efficacy endpoints, the pairwise comparisons for the difference in proportions of subjects between treatment groups and placebo group will be analyzed using the CMH test adjusted for previous biologic use, baseline corticosteroid use and baseline Adapted Mayo score (≤ 7 and > 7). Additionally, the CMH based two-sided 95% confidence interval (CI) for the difference in the proportions between the treatment groups and placebo group will be provided.

The non-responder imputation will be used for subjects with missing data at the endpoint evaluated. The last observation carried forward (LOCF) method will also be used as the sensitivity analyses for the secondary endpoints.

Continuous secondary efficacy variables will be analyzed using an Analysis of Covariance (ANCOVA) model including factors for treatment group and stratification variables. Baseline values will be used as a covariate in the ANCOVA models.

Both last observation carried forward (LOCF) and observed case (OC) analyses will be used for continuous endpoints when conducting ANCOVA analysis. The LOCF analysis is considered primary for inferential purposes. HCRU will be analyzed as observed only.

Continuous secondary efficacy variables with repeated measurements will also be analyzed using a Mixed Effect Model Repeated Measurement (MMRM). The baseline values to be included in MMRM are sex, age, disease duration, Baseline IMM use, Baseline hs-CRP. The comparison at a time point will be the contrast between treatments at that time point.

For HCRU, the number and percentage of hospitalizations and surgeries (all-cause and UC-related) will be calculated for each treatment group and placebo group. Differences

in the risk of hospitalization and surgeries will be compared between treatment groups and placebo group using Chi-square test.

